Subjects will receive Rapamycin or placebo for approximately two months. We will assess many parameters to assess changes due to the drug (RAPA), particularly in physiological systems known to change with aging, and will also measure indicators of health to ensure safe delivery of RAPA in the elderly cohort. Specifically, the tests to be run include the following: immune response to challenge with the trivalent seasonal influenza vaccine effects on the gut microbiome, perception of quality of life and depression, grip strength, timed walk, cognitive assessment, blood chemistry, immune and endocrine health, and other assessments of safe RAPA delivery. Some subjects may elect to participate in an optional imaging procedure to evaluate cerebral blood flow and metabolic rate of glucose using PET and MRI.

For Sub-study B Acarbose followed by Rapamycin

Subjects will receive ACA orally for approximately 2 months. The battery of tests outlined above (except immunization) will be performed at three time points (pre-ACA, after 2 months on ACA, and 1 month post-ACA termination), to measure the effects of ACA on the gut microbiome, basic blood metabolic markers, blood cell distributions, physical function parameters (including walking speed and grip strength), cognitive abilities, depression, cytokine levels, and blood cell function. ACA will be terminated and all subjects will be rested for approximately 1 month and will then enter the RAPA phase of study; they will be randomly assigned to either RAPA or placebo and will be maintained on the appropriate drug for a total of approximately 2 months. During that time, we will assess response to vaccine challenges and to other physiological measures, including those listed above. Subjects may also elect to participate in optional imaging procedures to evaluate cerebral blood flow and metabolic rate of glucose using PET and MRI.

For Sub-study C Acarbose alone

Subjects will be followed as in substudy B, but the tests will also be performed 1 month after termination of ACA.

For Sub-study D Rapamycin Alone – Cardiovascular Effects

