Step-by-Step Methods:**Methods for Sub-study A & B Rapamycin**

mTOR inhibition: Subjects will be randomized to mTOR inhibition by RAPA or placebo in equal sized groups. Those receiving the drug will be started on 1 mg per day with no loading dose. Dosage will be adjusted for a target whole blood concentration of 10-15 ng/ml and maintained there until the study's conclusion. RAPA blood levels will be determined by mass spec. The initial trough level will be drawn one week after initiation of therapy. When a maintenance dose is adjusted, the new dose will be maintained for 7 days before additional adjustments are made based on concentration monitoring. Reported adverse reactions to RAPA and related agents when used as solitary agents include mucositis, pneumonitis, skin rash, hyperlipidemia, hyperglycemia, thrombocytopenia, and anemia.

Clinical assessment: Subject health will be confirmed initially by history and physical exam, normal laboratory tests (fasting lipid profile, metabolic profile, CBC, and CK), and 12-lead EKG. Oral glucose tolerance test (OGTT): Baseline (fasting) samples for determination of glucose, insulin, and free fatty acid (FFA) concentrations will be drawn at -30, -15 and -0 min (these basal values are averaged). At time zero, each subject will ingest 75 g of glucose. Glucose, insulin and FFA are determined every 30 min for 2 h following glucose ingestion. The Matsuda index of insulin sensitivity will be calculated from OGTT results, as described (Matsuda and DeFronzo, 1999). At each visit, patients will receive a standard history, physical examination, blood chemistry assessment, and be queried in detail for RAPA adverse reactions including infections. A questionnaire (SF-36) designed to assess the benefits of health care interventions and the Geriatric Depression Scale questionnaire will allow us to characterize any adverse or beneficial effects. Between visits, subjects will be contacted weekly by the Clinical Nurse to ensure that no complications have arisen. Blood test for CK will be monitored.

If subjects have previously undergone all or part of screening labs/tests within the past 4 months, the data may be accepted for eligibility determination without screening labs or procedures having to be repeated.

Aim II. Assess the effects of mTOR inhibition on vaccine efficacy in the elderly.

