Immune parameters assessed and expected results We will focus on parameters known to change with age (Table 1) using blood collected after approximately 1, 6, and 8 weeks on RAPA or placebo, the following will be assessed and compared to levels determined prior to initiation of the treatment: i) Serum cytokine levels; Luminex-based assays will be used; these allow simultaneous measurement of 28 different cytokines. It is expected that RAPA will have the beneficial effect of decreasing the levels of pro-inflammatory cytokines (TGF- β , IL-12, IL-6, TNF- α). ii) Naive T cells are lost with aging due to thymus involution and a lifetime of clonal expansion of memory T cells. In mice, RAPA appears to protect these naive T cells which could then allow for a healthier immune response to “new” antigens in older individuals. To assess whether the same is seen in humans, PBMCs will be analyzed by FACS to assess the proportion of memory vs. naive T cells both before and after RAPA treatment. iii) T cell functional subsets will be assessed by FACS for cell surface markers and intracellular cytokines. Although expectations are less clear here, it will be important to assess whether RAPA has effects on human T cell development that are analogous to those seen in rodents. Moreover, these measurements have not previously been ascertained for human subjects in this advanced age group.

Aim IV. Determine whether mTOR inhibition can improve muscle strength and cognitive function

The following tests will be performed to assess RAPA affects on physiological parameters:

- 1) Grip strength (3 consecutive measurements by grip-strength dynamometer): participants will be seated in a chair with the forearm at a 90° elbow bend and 3 consecutive grip strengths will be completed with a standard grip strength dynamometer (in Kg) for the dominant hand. Results will be averaged for analysis.
- 2) Timed 40-foot walk: each participant will perform 3 walks (timed with a stopwatch) at their preferred walking speed over a measured 40-foot path. Results will be averaged for analysis.

Statistical comparisons will be made between measurements made before and after, as well as both within and between mTOR inhibited and placebo groups to test our hypothesis.

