Cognitive assessment: All subjects will undergo cognitive assessments within one week of their recruitment (before treatment) and at the end of treatment (approximately 2 months after entering the RAPA phase of the study). The cognitive tests will be selected from a battery of the following validated tests – EXIT, SLUMS, and/or TAPS – with care taken to avoid use of ones employed in the ACA phase (as appropriate) to limit the effects of “learning/memory”.

Results of the foregoing (grip strength, timed walk, and cognitive assessment scores) will be compared between groups.

Aim V. Assess the effects of RAPA on the gut microbiome.

Rationale Composition of the gut microbiota is known to change with age and this most likely contributes to increases in inflammation seen in older individuals. Given its broad effects on metabolic regulation and its oral delivery route, RAPA is likely to alter the gut microbiome and may thereby elicit changes in the host immune system (addressed in Aims II and III). In order to address this possibility, we will collect fecal specimens from the RAPA and placebo treated subjects at 4 time points, prior to RAPA treatment and after 1, 6, and 8 weeks on the drug. The gut microbiome will be characterized initially from the pre-treatment and 8 week treatment samples. The other fecal specimens will be stored for future analysis of the kinetics of interesting changes observed.

Approach The advent of next generation DNA sequencing has revolutionized efforts to characterize the endogenous microbiome. An oral medication, like RAPA, will likely target the gut microbiome. Thus, subjects will self-collect feces in sterile containers and deliver it to the clinic at their regular visits. DNA isolation will be performed by the Genomics Core facility on a fee-for-service basis and the samples will be delivered to the Sequencing Core Facility for analysis. The bacterial rDNA in each fecal sample will be amplified using primers from conserved regions of the 16S ribosomal RNA genes. Amplified DNAs are then used to generate a library which is subsequently subjected to deep (next gen) sequencing.

Sub-study B & C Acarbose

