Physical function will be assessed using two independent assays of parameters known to decline with age, handgrip strength and timed 40-foot walk. Performance measures will be done longitudinally at each clinic visit to offer the greatest potential to detect changes due to ACA treatment and subsequent withdrawal.

1) **Grip strength** (3 consecutive measurements by grip-strength dynamometer): participants will be seated in a chair with the forearm at a 90° elbow bend and 3 consecutive grip strengths will be completed with a standard grip strength dynamometer (in Kg) for the dominant hand. Results will be averaged for analysis.

2) **Timed 40-foot walk:** each participant will perform 3 walks (timed with a stopwatch) at their preferred walking speed over a measured 40-foot path. Results will be averaged for analysis.

Cognitive function will be assessed within one week of subject recruitment (before treatment), and at the end of treatment (2 months). These tests will be performed only twice to avoid learning effects that could confound the results. Three independent tests will be employed: EXIT (includes letter fluency) (13), SLUMS (St. Louis University Mental Status exam, which includes a memory test, digit span, and animal fluency) (14), GDS (Geriatr Depression Scale) and TAPS (Texas Assessment of Processing Speed; a digit/symbol coding test available in alternate forms to eliminate learning effects) (15). If significant improvement were seen with one (or more) of the cognitive measures, that test (or those tests) would be repeated at the end of the withdrawal period to assess longevity of the response. In addition, we will assess depression using the Geriatric Depression Score questionnaire.

CLOX Assessment: clock-drawing tests (CDT) as a screen for cognitive impairment at screening.

Immune function Blood will be collected from each subject before treatment and after two months on ACA. General parameters of immune health that are known to change with age will be assessed, as described below:

- 1) **Serum cytokine** levels will be determined using Luminex-based assays that allow simultaneous measurement of 27 different cytokines. It is known that aging is associated with an increase in the levels of pro-inflammatory cytokines (IL-12, IL-6, TNF- α), which contributes to the loss of immune regulation with age and increased susceptibility to certain pathogens. ACA reversal of this effect would be highly significant.

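### Aim IV, randomized RAPA phase (Sub-studies A and B): within-arm before/after change should not test the hypothesis; the planned between-arm test needs a stated form and, in Sub-study B, a post-acarbose baseline

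*Combined protocol and SAP*

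**What the plan says.** **Design.** Item 6, Methods for Sub-study A & B: "Subjects will be randomized to mTOR inhibition by RAPA or placebo in equal sized groups".

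**Comparisons.** Under Aim IV in Item 6, after the descriptions of grip strength and the 40-foot walk, comparisons are to be made "between measurements made before and after, as well as both within and between mTOR inhibited and placebo groups to test our hypothesis". After the cognitive paragraph the section adds: "Results of the foregoing (grip strength, timed walk, and cognitive assessment scores) will be compared between groups". Neither sentence ranks the comparisons. Neither says whether the between-arm one uses end values, changes or a baseline-adjusted difference. The Data Analysis Plan names no test. The only named method, repeated measures ANOVA, belongs to Aim D-2 in the uncontrolled Sub-study D.

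**The before value in Sub-study B.** All Sub-study B subjects first take ACA for about 2 months. Then "all subjects will be rested for approximately 1 month and will then enter the RAPA phase of study".
- Aim IV (Item 6) times cognitive testing "within one week of their recruitment (before treatment) and at the end of treatment".
- Item 2 gives three times for the Sub-study B battery, which includes cognition: "pre-ACA, after 2 months on ACA, and 1 month post-ACA termination".
- The ACA methods in Item 6 give two, before ACA and at 2 months: "These tests will be performed only twice to avoid learning effects that could confound the results". A repeat after withdrawal follows only if a test improved significantly.
- The visit schedule (Table 1 in Item 6), as extracted, marks grip, walk and cognition at V7, labelled week 0 for RAPA. Its footnote lets these tests be done over Visits 0 and 1.

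**Choice of cognitive test.** Aim IV selects from EXIT, SLUMS and TAPS, "with care taken to avoid use of ones employed in the ACA phase (as appropriate) to limit the effects of" learning. The ACA methods use all three.

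**The concern.** Randomization to placebo allows change caused by RAPA to be separated from change that would have happened anyway. A before/after comparison inside the RAPA arm gives that up. If it counts as a test of the hypothesis, a gain that placebo subjects share can be reported as support, and a shared decline can hide a real effect.

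The documents supply two possible sources of shared change. They acknowledge retest learning on the cognitive tests. In Sub-study B, every subject has also stopped ACA about a month before the RAPA phase, so carry-over in either direction is possible.

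The baseline question adds to this. If the recruitment score serves as the before value in Sub-study B, the within-arm change spans the ACA phase and contains any ACA effect.

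The pilot exists to supply data for larger studies, so a misattributed change would pass into their planning.

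**Working it through.** The plan gives no sample size, alpha, power or effect size for Aim IV, so there is no figure to reproduce. The following are **assumptions**: n = 10 or 20 per arm; two-sided 0.05 (2.5% in each tail); a shared change D in units of the SD of change; a true effect of 0.8 SD of change; and a baseline/follow-up correlation r.

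**1. False improvement within the RAPA arm, no drug effect.** Paired t, upper tail of the non-central t with n − 1 df and non-centrality D√n. For n = 10, D = 0.3, the non-centrality is 0.3 × √10 = 0.95 and the critical value is 2.262, giving 0.134.

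| Shared gain D | n = 10 | n = 20 |
|---|---|---|
| 0.1 | 0.047 | 0.062 |
| 0.3 | 0.134 | 0.246 |
| 0.5 | 0.293 | 0.564 |

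A shared decline of 0.3 gives the same rates of false worsening (0.134 and 0.246).

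**2. Either test counts.** If a significant within-RAPA or between-arm result (either direction) is taken as a finding, simulation with 40,000 trials per setting gives 0.084 at D = 0 and 0.321 at D = 0.5 for n = 10. For n = 20 it gives 0.085 and 0.584. The between-arm test alone stays at 0.048 to 0.052.

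**3. A real effect of 0.8 SD.** Within-arm detection is 0.616 (n = 10) or 0.924 (n = 20) with no shared change. A shared decline of 0.3 leaves D = 0.8 − 0.3 = 0.5, and detection falls to 0.293 or 0.564. The between-arm t test on change (2n − 2 df, non-centrality 0.8√(n/2), that is 1.79 or 2.53) has power 0.395 or 0.693 whatever the shared change.

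**4. Form of the between-arm test.** Variance relative to end values alone is 2(1 − r) for change and (1 − r²)(2n − 3)/(2n − 4) for ANCOVA. For n = 10, r = 0.5, ANCOVA gives 0.75 × 17/16 = 0.797.

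| r | Change | ANCOVA, n = 10 | ANCOVA, n = 20 | Saving vs change, n = 10 | Saving vs change, n = 20 |
|---|---|---|---|---|---|
| 0.5 | 1.00 | 0.797 | 0.771 | 20% | 23% |
| 0.7 | 0.60 | 0.542 | 0.524 | 10% | 13% |
| 0.9 | 0.20 | 0.202 | 0.195 | −1% | 2% |

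Against end values alone the ANCOVA saving is 20, 46 and 80% at n = 10. If an older recruitment value correlated only 0.3 with follow-up, that saving would be 3% (n = 10) or 6% (n = 20). In simulation the one-sided ANCOVA error rate was 0.024 to 0.028.

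**5. The Sub-study B baseline.** Two months of ACA plus one month of rest put a recruitment score about 3 months before RAPA starts. Item 2 and Table 1 imply a later cognitive score; the ACA methods make it conditional; Aim IV, read literally, does not use it. Because the ACA phase uses the whole RAPA-phase battery, the instruction to avoid its tests leaves the RAPA-phase test undetermined.

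**The case against.** The strongest reply is that the control is already planned. Subjects are randomized to placebo, and Aim IV compares all three measures between groups. The two sentences can be read together as between-arm change, with within-arm change reported alongside. This largely stands. A reader might infer that the plan has no controlled test, or that its between-arm test is biased without adjustment. The documents support neither.

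Other points that stand:
- The within-arm sentence sits under grip and walk, while the written cognitive comparison is between groups. For grip and walk in Sub-study A the documents name no source of shared change, so the rates above rest on assumed drift there.
- ANCOVA improves precision only, and against change scores the gain is modest or nil.
- The Table 1 footnote may mean only that entry testing is split over two visits. It does not say that V7 is skipped.
- Reducing the cognitive battery to one test would be a design change and is not needed.
- Aim III, as written, compares only with pre-treatment levels, but its rationale already frames the question in RAPA and placebo subjects. That is a wording gap, not a second fault.

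What the reply does not remove is that the text gives the within-arm comparison the role of testing the hypothesis and ranks nothing above it. Pilot status does not make a within-arm change interpretable. The conflict over cognitive timing is in plain prose, so it is not a product of text extraction.

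**Conclusion.** The concern holds in limited form and should be corrected. A valid between-arm comparison is planned, but its form is not stated, and a within-arm test that cannot isolate the drug effect stands beside it. In Sub-study B the cognitive before value is not reconciled across sections.

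The size cannot be derived from the documents, because arm size, shared drift, effect and correlation are all absent. Under the assumptions shown, false within-arm improvement runs from about 5% at a shared gain of 0.1 SD and 10 per arm to 56% at 0.5 SD and 20 per arm, against a nominal 2.5%. These are illustrations, not estimates of this trial's error rate, and the plan claims no confirmatory error control.

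That within-arm testing matters, and that the Sub-study B timing conflicts, follows from the text with high confidence. The reading of individual marks in Table 1 is less certain because the table is partly garbled.

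**What to change.** 1. State that the Aim IV test for grip, walk and cognition is RAPA versus placebo at end of treatment, by ANCOVA on the last value of the same measure before the first RAPA or placebo dose, with a confidence interval. Report within-arm changes descriptively.
2. In Sub-study B, take that baseline at V7, not at recruitment or Visit 0/1. In Sub-study A, a Visit 0/1 value may serve where the footnote is used.
3. Reconcile Item 2, Aim IV and the ACA methods in Item 6 with Table 1, so that Sub-study B cognition is scored at V7 and at end of treatment on the same test or tests from the existing battery. Use alternate forms of TAPS, which the protocol says exist.
4. Optionally, align the Aim III wording in the same way.

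**Cost.** Wording, and one degree of freedom per covariate. Grip and walk need no new measurement if the V7 marks in Table 1 are confirmed. Sub-study B cognition carries some repeat exposure to the tests, against the plan's aim of limiting learning. It needs one added session per subject only if the Aim IV and ACA-methods text, rather than Item 2 and Table 1, describes current practice. Learning shared by both arms does not bias the between-arm comparison.

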Physical function will be assessed using two independent assays of parameters known to decline with age, handgrip strength and timed 40-foot walk. Performance measures will be done longitudinally at each clinic visit to offer the greatest potential to detect changes due to ACA treatment and subsequent withdrawal.

1) **Grip strength** (3 consecutive measurements by grip-strength dynamometer): participants will be seated in a chair with the forearm at a 90° elbow bend and 3 consecutive grip strengths will be completed with a standard grip strength dynamometer (in Kg) for the dominant hand. Results will be averaged for analysis.

2) **Timed 40-foot walk:** each participant will perform 3 walks (timed with a stopwatch) at their preferred walking speed over a measured 40-foot path. Results will be averaged for analysis.

Cognitive function will be assessed within one week of subject recruitment (before treatment), and at the end of treatment (2 months). These tests will be performed only twice to avoid learning effects that could confound the results. Three independent tests will be employed: EXIT (includes letter fluency) (13), SLUMS (St. Louis University Mental Status exam, which includes a memory test, digit span, and animal fluency) (14), GDS (Geriatr Depression Scale) and TAPS (Texas Assessment of Processing Speed; a digit/symbol coding test available in alternate forms to eliminate learning effects) (15). If significant improvement were seen with one (or more) of the cognitive measures, that test (or those tests) would be repeated at the end of the withdrawal period to assess longevity of the response. In addition, we will assess depression using the Geriatric Depression Score questionnaire.

CLOX Assessment: clock-drawing tests (CDT) as a screen for cognitive impairment at screening.

Immune function Blood will be collected from each subject before treatment and after two months on ACA. General parameters of immune health that are known to change with age will be assessed, as described below:

- 1) **Serum cytokine** levels will be determined using Luminex-based assays that allow simultaneous measurement of 27 different cytokines. It is known that aging is associated with an increase in the levels of pro-inflammatory cytokines (IL-12, IL-6, TNF- α), which contributes to the loss of immune regulation with age and increased susceptibility to certain pathogens. ACA reversal of this effect would be highly significant.
- 2) **T_{REGs}** have been shown by us and others to increase with age. These cells function to suppress ongoing immune responses and their presence in older individuals correlates with diminished immunity (19). To address whether ACA can reverse this increase in T_{REGs}, PBMCs (peripheral blood mononuclear cells) will be analyzed by FACS to assess the proportion and number of CD4⁺CD25⁺foxp3⁺ cells (T_{REGs}). Future experiments (beyond this pilot grant) would then be needed to examine T_{REG} function and expression profiles.
- 3) **CD4/CD8 T cell ratio** is a parameter known to change with aging and HIV infection. Using flow cytometry of PBMCs, the ratio of CD4⁺ T cells / CD8⁺ T cells will be determined before, during, and after ACA.
- 4) **Naïve T cell numbers** decline with age due to thymus involution and a lifetime of clonal expansion of memory T cells. This contributes to the loss of immune competence leading to decreased efficacy of vaccines and increased susceptibility to infection in the elderly. The loss of naïve T cells among PBMCs will be analyzed by FACS at the 5 time points (before, during and after treatment) for both CD4⁺ helper T cell (T_H) and naïve CD8⁺ cytotoxic T cell (T_c) subsets. ACA induced recovery of naïve T cells would be significant.

Expected Results Statistical comparisons will be made between the pre-treatment time point and the post-treatment point (2 months on ACA). It is our hope that the ACA-induced extension of lifespan in mice will be echoed by improvements in all of the parameters measured which were selected due to their known deficiencies with aging. This would suggest simultaneous effects on three systems: immune, neuromuscular, and cognitive.

Aim VII. Assess the effects of ACA on the gut microbiome.

Rationale Composition of the gut microbiota is known to change with age and this most likely contributes to increases in inflammation seen in older individuals. Given its function in gastrointestinal metabolism, ACA is also likely to alter the gut microbiome; this may contribute to the beneficial effects of ACA on diabetic symptoms since it is known that changes in the resident microbes can impact both immune and endocrine functions. Although there were no searchable publications reporting characterization of the effects of ACA on the gut microbiome, there is a 2012 listing on *ClinicalTrials.gov*, entitled “Efficacy of acarbose on intestinal microbiome and incretins of Type 2 diabetes” from [name], Shanghai Jiao Tong University School of Medicine; no results have been posted to-date. Also, an abstract from the University of Alabama, Birmingham ([name]) reports on gut microbiome changes in mice treated with ACA [<http://www.uab.edu/medicine/camac/images/5-Abstract.pdf>]. Our hypothesis is that ACA will result in improvement of functions known to decline with age (immune, endothelial, cognitive, and neuromuscular). We further speculate that changes to the microbiome induced by ACA may play a role in mediating these pleiotropic effects. In order to address this possibility, we will collect fecal specimens from the ACA cohort and characterize the gut microbiome at the 2 time points prescribed above [pretreatment and after 2 months on ACA].

Approach The advent of next generation DNA sequencing has revolutionized efforts to characterize the endogenous microbiome. In fact, these genomic-based technologies have revealed many new bacterial species that were missed using microbiologic and serologic approaches. The endogenous microbiota plays a critically important role in generating an efficacious immune system and a healthy functioning gut. Of relevance to this proposal, the microbiome also regulates susceptibility to obesity and diabetes. An oral medication, like ACA, will likely target the gut microbiome. Thus, subjects will self-collect feces in sterile containers and deliver it to the clinic at their regular visits. DNA isolation will be performed by the Genomics Core facility on a fee-for-service basis and the samples will be delivered to the Sequencing Core Facility for analysis. The bacterial rDNA in each fecal sample will be amplified using primers from conserved regions of the 16S ribosomal RNA genes. Amplified DNAs are then used to generate a library which is subsequently subjected to deep (next gen) sequencing.

Expected Results For humans, there have been many reports documenting the bacterial species that dominate in older vs. young individuals (24). Given the ages of our subjects, we would expect to see a profile more similar to the “old” profile. It would be most exciting if ACA were to alter the microbiome, making it more “youthful”.

Sub-study D Rapamycin Alone – Cardiovascular Effects

For Aims D-1, D-2, D-3, and D-4:

Intervention with RAPA will begin at the end of Visit 2 once all screening and baseline measurements have been collected. Subjects will self-administer RAPA once daily for a period of 8 weeks (56 doses) and there will be no placebo group in this Sub-study. We will screen 12 MALE subjects to complete 6. No females will be enrolled in this pilot substudy.

Clinical assessment: See also Sub-study A (except without OGTT). In substudies A, B and C, no detrimental diabetogenic effects of RAPA were found, i.e. OGTT, FBS, HbA1c were unaltered by RAPA.

If subjects have previously undergone all or part of screening labs/tests within the past 4 months, the data may be accepted for eligibility determination without screening labs or procedures having to be repeated.

Physical function will be assessed using two independent assays of parameters known to decline with age, handgrip strength and timed 40-foot walk. Performance measures will be done longitudinally at Visits 2, 3, and 4 to offer the greatest potential to detect changes due to RAPA treatment.

1) **Grip strength** (3 consecutive measurements by grip-strength dynamometer): participants will be seated in a chair with the forearm at a 90° elbow bend and 3 consecutive grip strengths will be completed with a standard grip strength dynamometer (in Kg) for the dominant hand. Results will be averaged for analysis.

2) **Timed 40-foot walk:** each participant will perform 3 walks (timed with a stopwatch) at their preferred walking speed over a measured 40-foot path. Results will be averaged for analysis.

3) **Activity** will be continuously monitored in participants by wearing a Garmin Vivofit3 Activity Monitor. This battery operated, waterproof activity monitor will be worn continuously over the period of enrollment to record participant activity (steps per day, periods of sleep). The Garmin Vivofit and similar devices have been used successfully in other studies and have been found to be acceptable to older volunteer subjects {O'Brien, 2015 #2716;Schrack, 2016 #2715;Šimůnek, 2016 #2714}.

Immune function will be assessed pre-treatment and at the end of treatment (Visits 1 and 4). We will perform tests for serum cytokine profiles, flow cytometry with T cell subsets, and T cell activation potential.

Cognitive function will be assessed before treatment at Visit 2, and at the end of treatment (2 months, Visit 4). These tests will be performed only twice to avoid learning effects that could confound the results. Three independent tests will be employed: EXIT (includes letter fluency) (13), SLUMS (St. Louis University Mental Status exam, which includes a memory test, digit span, and animal fluency) (14), GDS (Geriatric Depression Scale) and TAPS (Texas Assessment of Processing Speed; a digit/symbol coding test available in alternate forms to eliminate learning effects) (15). If significant improvement were seen with one (or more) of the cognitive measures, that test (or those tests) would be repeated at the end of the withdrawal period to assess longevity of the response. In addition, we will assess depression using the Geriatric Depression Score questionnaire.

Aim D-1. Test whether RAPA treatment increases aortic compliance in elderly subjects.

Approach. PWV will be measured before, during, and at the end of RAPA treatment as per Table 2. Measurement of aortic PWV is the simplest way to assess arterial compliance non-invasively in humans and reflects the ability of the arterial system to cope with systolic ejection volume. It also implies that the compliant arterial system's major function is to relay cardiac contraction during diastole. Indeed, cardiac contraction lasts only one third of a cardiac cycle of the time. Due to the distension of the compliant large arteries during systole, after the end of cardiac contraction, the compliant large arteries return to their initial dimension and thereby help maintain blood flow. This phenomenon is of key physiological importance as diastolic flow in arteries may represent more than half of cardiac output. Large artery compliance represents the dynamic force opposing ejection (also called impedance): if high, it helps in ejection, the lower the compliance, diastolic facilitation of ejection is lessened. Many methods have been proposed to quantify this phenomenon. The simplest non-invasive approach to measure arterial compliance is PWV, i.e., the transit time measurement of the pulse wave from the aortic valve to the terminus of the aorta (1). We will use the SphygmoCor system, which has been used in successful large clinical trials and population surveys. This device uses a large band piezoelectric probe and allows the arterial pulse recording in succession (carotid then femoral), both signals being synchronized with the same time basis (ECG R wave) (1). We have such a device available and are experienced with its use in humans. To measure PWV, the subject will rest in supine position for at least 5-10 min to reach the physiological baseline conditions, the room will be maintained at a standardized temperature, and the blood pressure will be

accurately measured within minutes from the PWV recording times. Serial longitudinal measurements are performed as summarized in Table 2. All PWVs will be done in fasting condition. Overall, the reproducibility of PWV measurements is good (CV in the range of 8-12%) (1).

Expected Results-There are many reports documenting that the PWV is greater in older vs. young humans (1). Given the ages of our subjects, we expect to see a pattern of initially high PWV before RAPA treatment that would be reduced with RAPA. In the placebo group, we expect that their initially high PWV will be unaltered or increase during the study.

Aim D-2. Test whether RAPA treatment improves endothelial function in elderly subjects.

Approach. It is well known that microvascular endothelial dysfunction precedes dysfunction in conduit arteries and is predominantly due to reduced NO bioavailability in both aging and disease states. Choi, et al (2), have developed microvascular function test that reflects primarily NO-dependent vascular function and is thus of significant clinical utility. This test uses rapid local heating of forearm skin from 34°C to 39°C to produce a hyperemic vasodilation (an increase in cutaneous vascular conductance (CVC=LDF/MAP)) that is 80% dependent on NO. This is the most robust test of NO-dependent dilation that can be performed non-invasively in humans, as the multifold increase in conductance from 34°C to 39°C is almost entirely effected by NO. Due to the noninvasiveness and ease of performing the test, we will use rapid local heating to 39°C to assess NO-dependent dilation and thus microvascular function. Rapid local heating to 39°C elicits a plateau which reaches 50% of maximal CVC as effected by local warming to 42°C, which allows for assessment of interventions that may alter maximal vasodilatory mechanisms that are NO-independent. Upon arrival in the laboratory, subjects will be placed in a semi-supine position in a dialysis chair and be instrumented on their right forearm for laser-Doppler flowmetry measurements of skin blood flow (SkBF) with a LDF probe equipped with a local heating unit and thermocouple. A Finapres cuff placed on one finger for blood pressure measurements (MAP). Local skin temperature (Tloc) at the LDF site will be held at 34°C for approximately 5-10 minutes to establish a stable baseline measurement. Tloc will be then increased at a rate of 0.1°C/sec to 39°C and then held constant. After LDF has reached a stable plateau (30–40 min) at Tloc=39°C, Tloc will be raised to 42°C for about 30 min to maximally vasodilate the skin (9, 15, 17). For data analysis, CVC will be calculated. Averages of maximal absolute values of CVC (in mV) with Tloc=34, 39, and 42°C will be calculated and compared both within and between subjects by repeated measures ANOVA. All of the needed equipment is available in [name] lab.

Expected Results. It is well known that NO-dependent vasodilation is reduced in older vs. young individuals (5, 6). We expect that CVC responses to skin warming to 39°C will increase both during and after RAPA when compared to pre-RAPA responses.

****Depending on availability of subjects, shared lab equipment, and personnel resources, the vascular function assessments for baseline measurements of PWV and or LDF may be scheduled and performed at Visit 1 OR Visit 2 (see Table 2). This allows flexibility for the subject and facilitates protocol compliance for the research team.**

MRI Studies of Cardiac function and Cerebral Blood flow

Aim D-3. Examine whether mTOR inhibition improves diastolic function and increases cerebral blood flow in humans. We will explore whether mTOR inhibition with RAPA improves cardiac diastolic function and cerebral blood flow (CBF). Diastolic function and CBF will be measured by MRI **pre- and post-treatment with RAPA at Visits 2 and 4.**

Expected Results-There are reports that the cardiac function and CBF are improved in animal models by RAPA treatment {Chiao, 2016 #2623;Urfer, 2017 #2617}. Given the ages of our subjects, we expect to see a pattern of initially impaired diastolic function and CBF before RAPA treatment that would be improved with RAPA.

Aim D-4. Examine whether mTOR inhibition increases physical activity in humans.

Expected Results-RAPA treatment increases physical activity in animal models. {Miller, 2011 #1350;Urfer, 2017 #2617} . We anticipate that similar activity increases will be found in humans with RAPA administration.

Pilot data will be collected on at least 6 subjects to analyze whether treatment with RAPA increases physical activity. Using a Garmin Vivofit3 Activity Monitor [Garmin, Inc.] provided by the study to each participant. we will examine whether RAPA effects overall activity by measuring time, distance, step count, calories burned, total hours of sleep, periods of movement, and periods of restful sleep. Subjects will wear activity monitors continuously for approximately 2 weeks from consent to baseline visit at which we will download pre-intervention activity levels. Subjects continue wearing bracelet-style activity monitors throughout the study duration and upon returning to the clinic (4 weeks and 8 weeks of RAPA treatment), provide data downloads at each of the Visits 3 and 4. Participants will keep the activity

tracking devices after the study is complete as a thank-you for their participation {O'Brien, 2015 #2716;Schrack, 2016 #2715;Šimůnek, 2016 #2714}.

Data Analysis Plan:

